## 3) Corrected Calcium

Corrected Calcium is derived using the following formula:

$$CA_{corr} [mmol/l] = Serum Calcium [mmol/l] + 0.02 \times (40 [g/l] - Albumin [g/l])$$

### 4.9.6 Vital Signs

Vital signs will include measurement of body temperature (oral, rectal, axillary, or tympanic), heart and respiratory rates, blood pressure and weight. Height will be only measured at selected visits. Vital signs data together with their change from baseline will be summarized descriptively over time.

### 4.10 **BIOMARKER**

Data from pharmacodynamics (PD), safety biomarker, safety coagulation system biomarker will be analyzed descriptively with summaries over time. Summary statistics, will include arithmetic and geometric means (if appropriate), median, range, and standard deviations.

At least the following safety biomarkers, safety coagulation system biomarkers, and PD biomarker will be analyzed:

**Table 2: List of analyzed biomarkers**

Factor VIII Inhibitor, chromogenic	CBU
Factor VIII Activity, chromogenic	U/dL
Activated Partial Thromboplastin Time	sec
D-Dimer	ug/mL (FEU)
Factor IX, concentration	ug/mL
Factor X, concentration	ug/mL
Prothrombin fragment 1+2	ng/mL
Prothrombin INR	Fraction of 1
Fibrinogen	g/L

All parameters are quantitative

Outputs to be produced for selected biomarkers and FVIII inhibitor titer are as follows (Table 3: List of outputs to be generated for biomarkers and FVIII inhibitor titers). Additional detail for each lab parameter is provided below.

**Table 3: List of outputs to be generated for biomarkers and FVIII inhibitor titers**

Output	FIX Antigen	FX Antigen	FVIII Inhibitor titer	Pro-thrombin INR	D-dimer	aPTT (not diluted)	Reported FVIII Activity	Pro-thrombin fragment	Fibrinogen
Biomarker Test Results and Change from Baseline by Visit	X	X	X	X	X	X	X	X	X
Plot of Mean and Individual <Biomarker> over Time by Treatment Group	X	X		X		X	X		
Plot of Median and Individual <Biomarker> over Time by Treatment Group			X		X			X	X
Categorical summary over time				X					
Listing	X	X	X	X	X	X	X	X	X

The following specific data handling rules are used in plots and descriptive summaries. Listings will include the original values.

- FVIII activity: for any value reported as <1% use 0.5 (LLOQ/2)
- D-dimer: for any value reported as <0.36 use 0.18 (LLOQ/2)
- aPTT: for any value reported as >255 exclude from analysis and add footnote "If clotting not detected, the sample is excluded from the analysis"

The bone and joint biomarkers may be analyzed later and presented in a separate report.

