#### **4.5.6.5 Anti-emicizumab Antibodies**

Plasma samples are required for immunogenicity assessments to detect anti-emicizumab antibodies. Additional samples to detect anti-emicizumab antibodies may also be drawn at the time of hypersensitivity events or following suspected loss of efficacy. Samples will be analysed at the central laboratory.

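### SAP 4.10 leaves aPTT results above 255 s out of plots and summaries; if any occur, the summarised aPTT and its fall from baseline are understated by an amount the outputs do not reveal

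*SAP*

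**What the plan says.** The rule sits in the data-handling list under Table 3 of SAP 4.10. For aPTT it reads "for any value reported as >255 exclude from analysis and add footnote", and the footnote to be printed is "If clotting not detected, the sample is excluded from the analysis". The scope is stated just above: "The following specific data handling rules are used in plots and descriptive summaries. Listings will include the original values".

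The two rules before it treat censored results differently. For FVIII activity, "for any value reported as <1% use 0.5 (LLOQ/2"); for D-dimer, "for any value reported as <0.36 use 0.18 (LLOQ/2"). Those results stay in the summaries at half the lower limit.

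Table 3 assigns aPTT three outputs: results and change from baseline by visit, a listing, and the row "Plot of Mean and Individual <Biomarker> over Time by Treatment Group". It is not marked for the median plot or the categorical summary. SAP 4.10 asks for arithmetic and (where suitable) geometric means, median, range and standard deviation. Nothing asks for the number of excluded aPTT results at each visit, or for a sensitivity analysis that keeps them.

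**The concern.** A result above 255 s is informative: the clotting time is at least that long. Removing it is selection on the outcome, so the direction of the error is known. Protocol 5.1.3 states that emicizumab normalises aPTT even at sub-therapeutic levels, so very long times are to be expected before dosing, if at all, or if the drug's effect on the assay were to vanish.

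Three consequences follow if such samples exist. The summarised aPTT at that visit is too short. Patients whose baseline exceeded 255 s have no usable baseline and leave the change-from-baseline table, although theirs are the longest starting values. A post-baseline result that goes back above 255 s appears in neither the table nor the plots. Because no count is reported by visit, someone reading the table cannot tell whether the error is nil or large.

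**Working it through.** **Inputs from the documents.** Upper limit 255, in seconds (SAP Table 2 gives the aPTT unit); about 200 patients (SAP 2.3). PD samples are first scheduled at Week 1 (Protocol Appendix 2), so no screening aPTT is scheduled that could stand in for a lost baseline. SAP 4.9.5 requires both baseline and visit values for change from baseline; that rule is written for laboratory data, and I assume it applies to biomarkers too.

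**Plan's own figures.** The documents derive nothing from the 255 cut-off, so there is no stated result to reproduce. The neighbouring substitutions are correct: 1/2 = 0.5 and 0.36/2 = 0.18.

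**Step 1: a floor that needs no distribution.** Let k of n samples exceed 255 and let the kept samples have mean m. The full mean minus the reported mean is (k/n) × (mean of the excluded − m), which is at least (k/n) × (255 − m). With n = 200:

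| k above 255 | m = 80 s | m = 100 s | m = 150 s |
|---|---|---|---|
| 0 | 0 | 0 | 0 |
| 2 | 1.8 s | 1.6 s | 1.1 s |
| 5 | 4.4 s | 3.9 s | 2.6 s |
| 10 | 8.8 s | 7.8 s | 5.2 s |
| 20 | 17.5 s | 15.5 s | 10.5 s |

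The values of k and m are assumptions.

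**Step 2: size under an assumed lognormal baseline.** Let p be the share above 255, s the log-SD and z the upper-p normal quantile. Then μ = ln 255 − z·s, and the kept mean is m = exp(μ + s²/2) × Φ(z − s)/(1 − p). The floor is p × (255 − m). Example with s = 0.4, p = 5%: z = 1.645, exp(μ + s²/2) = 143.1, Φ(1.245)/0.95 = 0.940, so m = 134.5 and the floor is 0.05 × 120.5 = 6.0 s. The last column divides the floor by the fall from the capped mean (m + floor) to an assumed 30 s on treatment.

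| p | Floor, s = 0.4 | Floor, s = 0.6 | Share of the fall lost |
|---|---|---|---|
| 1% | 1.5 s | 1.8 s | 2–4% |
| 5% | 6.0 s | 7.6 s | 5–10% |
| 10% | 10.6 s | 13.7 s | 8–13% |
| 20% | 17.9 s | 23.6 s | 12–18% |
| 30% | 23.8 s | 31.6 s | 14–21% |

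The share lost assumes that patients with the longest baselines fall to about the same on-treatment level as the rest.

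**Step 3: the median.** The median of the kept samples is exp(μ + s·z′), with z′ the normal quantile at (1 − p)/2. At p = 5% the median falls from 132.1 to 128.8 s (s = 0.4) or from 95.0 to 91.5 s (s = 0.6). Ranking results above 255 as highest would leave it unbiased while fewer than half are censored.

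**Step 4: later visits.** Illustration: 4 of 200 samples above 255 and the rest averaging 30 s give at least (196 × 30 + 4 × 255)/200 = 34.5 s, where the plan would report 30 s. Now suppose instead that 5% of patients lose the effect and return to their own baseline, with 5% of baselines above 255. In simulation about 95% of those patients remain in the summary, and the rise in the mean is 6.0 s rather than 6.7 s (log-SD 0.3) or 4.1 s rather than 4.9 s (log-SD 0.5). Most of that signal survives.

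**The case against.** The strongest reply is that the size is wholly assumed. The documents give no aPTT distribution and no count above 255. With none the rule does nothing, and at 1% it costs under 2 s in the capped comparison. Shares of 20–30% would need a median baseline of about 154–207 s, which nothing in the documents supports. This stands, and it limits the point to a conditional one.

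The rule is also pre-specified, footnoted and confined to plots and summaries, and SAP 4.10 already asks for the median and range. This stands in part. That median and range are computed after exclusion, so the reported maximum can never exceed 255, and the footnote carries no count.

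Whether the laboratory regards a no-clot result as a valid long time or as a failed measurement is not stated. That is a fair reservation, but the rule removes all such results without distinguishing the two. The contrast with the half-limit substitutions is also looser than it looks: a low result lies between zero and the limit, whereas one above 255 has no upper bound. Capping therefore cannot make the mean unbiased, which is a reason to prefer the median.

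A reader might go further and infer that the aPTT curve cannot show patients in whom the effect disappears. The documents do not support that: a return to a prolonged time below 255 s stays in the table and plots, and since aPTT normalises at sub-therapeutic levels, partial loss may not show under any rule.

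**Conclusion.** The point holds in conditional form. If any aPTT sample reads above 255 s, the rule shortens the mean and median at that visit, drops the longest baselines from change from baseline and so understates the fall, and hides returns above 255 s. The direction for the visit summaries needs no distributional assumption. The understated fall also assumes that patients with the longest baselines do not stay correspondingly longer on treatment. The size cannot be given from the documents: it is zero with no such samples and otherwise at least (k/n) × (255 − m) for the mean. The 1.5–1.8 s and 6–32 s figures rest on the assumed lognormal shape, log-SD 0.4–0.6 and shares of 1% and 5–30%.

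The consequence is limited to a descriptive PD biomarker. Two larger readings should not be drawn. One is that a lead PD marker is compromised: the objectives table has no PD endpoint, and Protocol 3.3.4 says the identity of effective PD biomarkers is not yet settled. The other is that the rule obstructs the anti-emicizumab antibody objective: Protocol 6.6 and SAP 4.8 relate antibody status to safety, efficacy and PK, not to aPTT.

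**What to change.** In SAP 4.10, replace the aPTT rule as follows.

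- Retain results above 255 as above the upper limit. For any mean, set them to 255 and state in a footnote that the mean is then a lower bound.
- Report the number and percentage above 255 at each visit.
- Present median and quartiles with these results ranked highest, and move aPTT to the median-plot row of Table 3.
- Exclude only samples that the laboratory flags as technically invalid.

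The cost is a change of SAP wording and one programming change. No new data are needed, since the listings already hold the original values. The one drawback is that a mean with capped values remains a lower bound, which the footnote discloses.

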#### 4.11 MISSING DATA

The following rules will be used to impute missing data:

- In order to implement the 72-hour rule, it is assumed that the bleeds and treatments with missing time occurred at 12:00 (noon).
- If, on a given day, the treatment time is partial and the bleed time complete, the partial time is assumed to be the same as the complete time. In case of multiple events per day, the last complete time is used.
- All bleeds with an anatomical location in a joint are considered joint bleeds
- All bleeds with missing cause are included as spontaneous bleeds
- If a bleed which was entered through the hand held device was edited through a Data Clarification Process (bleed type changed from other/muscle to joint), it is possible to leave the symptoms unanswered. In this case, the bleed should count as a joint bleed.

See also endpoint definitions for specific data handling rules.

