### **2.2.2.2 Treated bleeds**

A bleed is considered to be a “treated bleed” if it is directly followed (i.e., there is not an intervening bleed) by a hemophilia medication reported to be a “Treatment for bleed” (see Haemophilia Medication Record) irrespective of the time between the treatment and the preceding bleed. Note, a bleed occurring at the same time as a treatment, counts as a treated bleed. A bleed and the first treatment thereafter are considered to be pairs (i.e., one treatment belongs to one bleed only), with the following exception: if multiple bleeds occur on the same calendar day, the subsequent treatment is considered to apply for each of these multiple bleeds.

Bleeds due to surgery/procedure will not be included in the primary analysis. In addition, treatments reported as “Treatment for bleed” directly following a bleed due to surgery/procedure are excluded.

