### **2.2.2.4 All bleeds**

“All bleeds” comprise both treated and non-treated bleeds. In this definition, all bleeds are included, irrespective of treatment with coagulation factors, with the following exception: bleeds due to surgery/procedure are excluded, as in the primary analysis.

The 72-hour rule will be applied to the “All bleeds” endpoint. For treated bleeds, it will be implemented exactly as defined in Section 2.2.2.2. For non-treated bleeds (not followed by any treatments with coagulation factors before the recording of a subsequent bleed), it will be implemented by calculating the interval of 72 hours from the bleed itself. Non-Treated bleeds are bleeds not covered by the definition of treated bleeds for the primary endpoint. To clarify, one bleed can be a composition of treated and non-treated bleeds.

Examples:

RE - 2h – T\* – 75h – RE – 2h - T -> 2 bleeds (\*72h calculated from last treatment)

RE\* - 75h – RE – 2h - T -> 2 bleeds (\*72h calculated from bleed because there is no treatment)

RE – 70h – RE – 2h - T -> 1 bleed

RE - 50h – RE – 30h – RE -> 1 bleed

RE – 30h – RE - 25h – LE -> 2 bleeds

RE – 2h – T – 3h – T\* – 35h – RE – 2h – LE\*\* – 45h – LE- 70h - RE -2h -T -> 3 bleeds (\*72h calculated from last treatment, \*\* calculated from previous bleed due to no treatment)

RE=right elbow bleed, LE=left elbow bleed, T=treatment for bleed

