#### **4.6.1.1 Bleeds**

The primary analysis will be based on treated bleeds (see definition 2.2.2.2). The number of bleeds over time will be estimated using a negative binomial (NB) regression model, which accounts for different follow-up times. The time that each patient stays in the study (efficacy period) will be included as an offset in the model.

An additional model which adjusts for number of bleeds (< 9 or ≥ 9, according to eCRF) in the last 24 weeks prior to study entry will be used to support the primary analysis.

In the rare case that the negative binomial model does not converge or no bleeds were observed for a given endpoint, the primary analysis will be based on “calculated” annualized bleed rate (ABR).

The ABR is calculated using the following formula (called Calculated ABR on all outputs):

$$\frac{\text{Number of bleeds during the efficacy period}}{\text{Number of days during efficacy period}} \times 365.25$$

The efficacy analyses will include the following endpoints defined in section 2.2.2: treated bleeds, all bleeds, treated joint bleeds, treated target joint bleeds and treated spontaneous bleeds. For each endpoint, the model based ABR will be estimated along with its corresponding 95% CI. In addition, the mean, 95% CI based on Exact Poisson, median, IQR, min and max will be provided for the calculated ABR.

A corresponding listing will be provided which will include for each patient the duration of efficacy period, number of bleeds together with calculated ABR for treated bleeds, all bleeds, treated spontaneous bleeds, treated joint bleeds and treated target joint bleeds (based on data before up-titration only). A separate listing will also be provided for the up-titrated population, based on data on or after the up-titration.

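### SAP 4.11 places a bleed with no recorded time at noon, so a bleed treated earlier that day can be counted as untreated

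*SAP*

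**What the plan says.** SAP 4.11 gives two timing rules. The first is introduced as a step towards applying the 72-hour rule: "it is assumed that the bleeds and treatments with missing time occurred at 12:00 (noon". The second aligns times within a day, in one direction only: "If, on a given day, the treatment time is partial and the bleed time complete, the partial time is assumed to be the same" as that of the bleed. No rule covers a missing bleed time with a complete treatment time. SAP 4.11 also points to the endpoint definitions, but nothing in SAP 2.2.2 deals with a treatment timed before its bleed.

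SAP 2.2.2.2 counts a bleed as treated "if it is directly followed (i.e., there is not an intervening bleed) by a hemophilia medication reported to be a" treatment for a bleed, with no limit on the delay. Ties are settled explicitly: "Note, a bleed occurring at the same time as a treatment, counts as a treated bleed". Pairing runs forward: "A bleed and the first treatment thereafter are considered to be pairs". The one exception is that several bleeds on the same calendar day share the next treatment.

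The 72-hour rule in SAP 2.2.2.3 runs from the last treatment of the first bleed and relies on the same pairs. A bleed that fails the definition falls to the other class under SAP 2.2.2.4: "Non-Treated bleeds are bleeds not covered by the definition of treated bleeds for the primary endpoint". SAP 4.6.1.1 then states: "The primary analysis will be based on treated bleeds (see definition 2.2.2.2".

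**The concern.** An imputed time can override the patient's own report that an infusion was given for a bleed. Protocol 4.5.7.1 defines a bleed by coagulation factor having been given to treat it and sets no condition on clock order. The existing alignment rule shows that this kind of problem was foreseen, but only for a missing treatment time.

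At stake is the count of treated bleeds, on which the main bleed analysis rests, together with its joint, target-joint and spontaneous subsets (SAP 2.2.2.7 to 2.2.2.9). A patient can also move into the zero-bleed category (SAP 4.6.1.2 and 4.6.5). The morning infusion is either left without a bleed or attached to an earlier one, which disturbs the per-bleed summaries of infusions, dose and treatment duration (SAP 4.6.1.6 and 4.9.1.2). The sensitivity analyses in SAP 4.6.6 do not vary the imputed time.

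**Working it through.** **Rules applied.** Sort bleeds and treatments by time. On a tie the bleed comes first, so it is treated. Each treatment goes to the preceding bleed, and same-day bleeds share it. Two bleeds at one site are merged if the second falls within 72 hours of the first bleed's last treatment, or of the first bleed itself if it was untreated.

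**The SAP's own examples (2.2.2.4).** RE and LE are right and left elbow.

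1. RE, treatment, 75 h, RE: 75 > 72, so 2.
2. RE untreated, 75 h, RE: 75 > 72, so 2.
3. RE untreated, 70 h, RE: 70 ≤ 72, so 1.
4. Three RE bleeds, gaps of 50 h and 30 h: 1.
5. RE, 30 h, RE, then LE: 1 + 1 = 2.
6. The second RE comes 35 h after the last treatment, so it merges. The two LE bleeds are 45 h apart, so they merge. The last RE comes 2 + 45 + 70 = 117 h after the previous, untreated RE, so it is new. Total 3.

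These match the stated counts of 2, 2, 1, 1, 2 and 3.

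**The case at issue.** The bleed time is missing, so the bleed is set to 12:00. The clock times below are illustrative.

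| Case | Treatment records | Treated bleeds, true order | Treated bleeds, SAP as written |
|---|---|---|---|
| a | one at 09:00 (true bleed 08:00) | 1 | 0 |
| b | 09:00 and 15:00 | 1 | 1, but the 09:00 infusion is not linked to this bleed |
| c | one at 14:00 | 1 | 1 |
| d | time also missing (both at 12:00) | 1 | 1, by the tie rule |
| e | as (a), with an untreated bleed elsewhere five days before | 1 | 1, but the earlier bleed is the one flagged |
| f | as (a), with a treated bleed elsewhere five days before | 2 | 1, and the 09:00 infusion joins the earlier bleed |

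The all-bleeds count is the same either way: 1 in (a), 2 in (e) and (f).

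**Why one direction is safe.** Take a bleed at 15:00 whose treatment has no clock time. With the existing alignment rule the treatment moves to 15:00 and the bleed is treated (1). With noon imputation alone the treatment would precede the bleed (0).

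**With the mirror rule.** In (a) the bleed moves to 09:00, ties with its treatment and is treated (1).

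**Size per lost bleed.** SAP 4.6.1.1 defines calculated ABR as bleeds ÷ days × 365.25. One bleed fewer changes it by:

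- two years: 1 ÷ 730.5 × 365.25 = 0.5
- one year: 1 ÷ 365.25 × 365.25 = 1.0
- a 24-week interval: 1 ÷ 168 × 365.25 = 2.17

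**The case against.** Four points on the other side carry weight.

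- **Scope.** The noon rule is introduced for the 72-hour rule, and treated status is defined elsewhere, by sequence. Using noon to decide treated status is therefore an inference. It is a reasonable one, because the 72-hour rule needs the same pairs and the SAP gives no other time for ordering them.
- **Frequency.** Patients are asked for start and stop times, and investigators review the records for completeness. Missing times may be few. Neither document gives a figure.
- **Direction.** Noon imputation can also err upwards. An untreated evening bleed with no recorded time, moved to noon, can pick up an afternoon infusion given for something else.
- **Consequence.** Efficacy is a secondary objective and all analyses are descriptive. The event still counts under all bleeds, a sensitivity analysis uses every recorded bleed, and the listing in SAP 2.2.2.3 shows bleeds beside medication. These make the error visible but do not correct the treated ABR.

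A reader might infer that every bleed with a missing time and a morning treatment is lost. The text does not support that. A later treatment for a bleed, even on the next day, keeps the bleed treated if no other bleed intervenes (case b). An earlier untreated bleed can absorb the infusion and leave the total unchanged (case e).

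**Conclusion.** The gap is real. A bleed with a missing time whose treatment was recorded before noon that day is placed after that treatment. It counts as non-treated unless another treatment for a bleed follows before the next bleed. In this scenario any count lost lowers the treated ABR: by 0.5 for that patient over two years, more over shorter periods. All bleeds is unaffected.

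This rests on noon being used for pairing as well as for the 72-hour window. A reader might go further and infer a material bias in favour of emicizumab. The documents do not support that: they give neither the frequency of missing bleed times nor the share of treatments given before noon, and errors in the other direction are possible. The net effect on ABR is unknown and may be small. The change is still worth making, because a stated rule gives a wrong result on the main bleed endpoint and the remedy is cheap.

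**What to change.** Add the mirror rule to SAP 4.11: if the bleed time is missing and a same-day treatment for a bleed has a complete time, set the bleed time to the earliest such treatment time, and use noon only when neither time is known. The earliest time keeps all of that day's infusions with the bleed. The sentence should say that it departs here from SAP 4.11's convention of using the last complete time when there are several events in a day.

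Add two safeguards. Where an earlier bleed is still within its 72-hour window, query or flag the record before reassigning the infusion. State that imputed times also apply to the pairing in SAP 2.2.2.2.

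The cost is a few sentences in the SAP, a small programming change and some queries. The downside is that a repeat dose for an earlier bleed could occasionally be tied to the new bleed; the flag is there to catch that. The rule does not remove the upward error described above.

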### **2.2.2.3 72-Hour rule**

Two bleeds of the same type (e.g., “joint,” “muscle,” or “other”) and the same etiology and at the same anatomical location are considered to be one bleed if the second occurs within 72 hours from the last treatment for the first bleed. Any bleed with a different etiology is considered a separate bleed regardless of time from last injection. The last treatment is defined as the last treatment before a new bleed occurs, either in the same or in a different location. This is in-line with the above definition that bleeds and treatments are considered to be pairs.

If the bleed location is other/other, other/other is used as the bleed location and not the exact location entered on the separate eCRF page.

In case of trauma with multiple different locations of bleed, this will be considered as one bleed for the analyses. However, all data will be collected, including the various locations of the different bleeds.

A listing of all bleeds is produced. The listing includes all bleed and hemophilia medication, except emicizumab, information entered on the Bleed Record, with an indicator which bleeds are included in the primary analysis and which do not count as separate bleeds due to the 72h rule.

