### 2.2.2.6 Definitions of Cause/Classification of Bleeds

Bleed assessments will be separated into spontaneous bleeds, traumatic bleeds, and bleeds related to procedures. Both spontaneous bleeds (i.e., the occurrence of hemorrhage where neither the patient nor a caregiver can identify a reason) and traumatic bleeds (i.e., hemorrhage occurring secondary to an event such as trauma, “strenuous” activity, or “overuse”) will be collected. The definitions for the different type of bleeds are as follows:

- **Spontaneous bleeds.** Bleeds will be classified as spontaneous if a patient records a bleed when there is no known contributing factor such as definite trauma, antecedent “strenuous” activity, “overuse”, or procedure/surgery. The determination of what constitutes “strenuous” or “overuse” will be at the discretion of the patient. For example, light jogging may be considered “non-strenuous” while sprinting may be considered “strenuous”; lifting of weights for a short period of time may be considered “moderate use” while repetitive weightlifting may be considered “overuse”.
- **Traumatic bleeds.** Bleeds should be classified as traumatic if a patient records a bleed when there is a known or believed reason for the bleed. For example, if a patient were to exercise “strenuously” and then have a bleed in the absence of any

obvious injury, the bleed would be recorded as a traumatic bleed because, although no injury occurred, there was antecedent “strenuous” activity. Bleeds with preceding injuries would certainly be classified as traumatic. In addition, bleeds related to surgery, such as hematomas resulting from any surgeries, will also be classified as traumatic bleeds. Bleeds related to surgeries will not be associated with any trauma except surgery-induced trauma.

- **Bleeds related to procedures.** This category would include hematomas resulting from any invasive procedure (e.g., tooth extractions, venipuncture, or SC drug administrations) or invasive diagnostic procedures (e.g., lumbar puncture, arterial blood gas determination, or any endoscopy with biopsy, etc.) or surgeries. Any instances of these bleeds would not be counted as bleeds in the context of the study, but the relevant data will be collected. Bleeds related to procedures will not be associated with any trauma except procedure-induced trauma.

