#### **4.6.1.4 Type of trauma**

Type of trauma will be summarized according to the categories on the eCRF. The traumas are analyzed separately for bleed related trauma and non-bleed related trauma including all trauma. Non-bleed related trauma are identified through bleed number=ND on the trauma form.

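### SAP 4.11 counts every bleed with a missing cause as spontaneous, even where the trauma form links that bleed to an injury (minor)

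*SAP*

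**What the plan says.** SAP 4.11 opens with "The following rules will be used to impute missing data", and one of its bullets reads "All bleeds with missing cause are included as spontaneous bleeds". No exception is attached, and no count of the affected bleeds is asked for. The section ends with "See also endpoint definitions for specific data handling rules", but none of the bleed definitions in SAP 2.2.2 fills a missing cause from another form.

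Five other places bear on this:

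- **SAP 2.2.2.6** defines the label: "Bleeds will be classified as spontaneous if a patient records a bleed when there is no known contributing factor such as definite trauma". It adds: "Bleeds with preceding injuries would certainly be classified as traumatic".
- **SAP 4.6.1.4** analyzes bleed-related and other trauma separately: "Non-bleed related trauma are identified through bleed number=ND on the trauma form".
- **SAP 2.2.2.3** merges two records only when type, etiology and location agree and the second falls inside the 72-hour window. Otherwise, "Any bleed with a different etiology is considered a separate bleed regardless of time from last injection".
- **SAP 2.2.2.9** selects the spontaneous bleeds first and applies the 72-hour rule afterwards.
- **SAP 4.6.1.1** makes treated spontaneous bleeds one of five annualized bleed rate (ABR) endpoints. They appear again in SAP 4.6.1.2 (categories) and SAP 4.6.5 (12- and 24-week intervals).

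**The concern.** The ND code on the trauma form marks trauma that led to no bleed, so the form has a bleed-number field and other entries can be tied to a bleed. When a bleed with a blank cause is tied to an injury in this way, a contributing factor is known and SAP 2.2.2.6 makes the bleed traumatic. SAP 4.11 nevertheless calls it spontaneous. Elsewhere the same section does use another collected field: anatomical location settles whether a bleed is a joint bleed.

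Two things are at stake. The treated spontaneous rate would depend partly on how often cause is left blank. In addition, etiology is a matching key in the 72-hour rule, so a wrong label may change how many bleeds are counted. None of the sensitivity analyses in SAP 4.6.6 varies the missing-cause rule.

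**Working it through.** **1. Reproduce the SAP's own figures.** The only stated figures that bear on this are the six worked examples of the 72-hour rule in SAP 2.2.2.4. I matched records on location and etiology, and ran the clock from the last paired treatment, or from the bleed itself if untreated. The counts are 2, 2, 1, 1, 2 and 3, as printed.

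**2. Put a trauma-linked blank through the same rule.** Each sequence is a right-elbow bleed treated at 2 hours, then a right-elbow record 40 hours after that treatment with cause blank but a linked trauma entry.

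| First bleed | Count using the linked cause | Count if the blank is set to spontaneous |
|---|---|---|
| Traumatic | 1 (0 spontaneous) | 2 (1 spontaneous) |
| Spontaneous | 2 (1 spontaneous) | 1 (1 spontaneous) |

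The first row is a wrong split and the second a wrong merge. The net effect on treated-bleed and all-bleed counts therefore has no fixed sign.

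**3. Direction for the spontaneous endpoint.** Because SAP 2.2.2.9 selects before merging, the error here is the extra record that enters the selection, not the split. It adds one bleed unless it lies within 72 hours of a spontaneous bleed at the same site, when it is absorbed (second row). In an unusual chain it could even join two spontaneous bleeds: with same-site records at 0, 60 and 120 hours, a mislabelled middle record bridges the outer two. Apart from such cases the bias is upward.

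**4. Illustrative size.** Inputs from the BH29884 emicizumab arm (protocol 1.2.2.3): treated ABR T = 2.9 and treated spontaneous ABR S = 1.3, so T − S = 1.6. These are model-based rates, so the difference is approximate. Two assumptions are needed, neither given in the documents: m, the share of non-spontaneous treated bleeds with no cause, and f, the share of those with a trauma link.

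- Under the SAP rule: S + m(T − S)
- After using the link: S + m(1 − f)(T − S)

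| m | SAP rule | After fix, f = 0.5 | After fix, f = 1 |
|---|---|---|---|
| 1% | 1.316 (+1.2%) | 1.308 | 1.30 |
| 2% | 1.332 (+2.5%) | 1.316 | 1.30 |
| 5% | 1.38 (+6.2%) | 1.34 | 1.30 |
| 10% | 1.46 (+12.3%) | 1.38 | 1.30 |
| 20% | 1.62 (+24.6%) | 1.46 | 1.30 |

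For m = 5%: 1.3 + 0.05 × 1.6 = 1.38; with f = 0.5, 1.3 + 0.05 × 0.5 × 1.6 = 1.34. Merging under the 72-hour rule is ignored here. The part due to ignoring the trauma form is the SAP-rule column minus the after-fix column: at 5%, 0.04 if half are linked, 0.08 if all are, and nothing if none are.

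**The case against.** **The case may rarely or never arise.** The documents do not show the form logic, so it is not established that a bleed with a blank cause can have a linked trauma entry. This stands and makes the point conditional. It is weakened because the form also takes trauma unconnected with any bleed, so it is not opened only by entering a traumatic cause.

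**The 72-hour link is an inference.** In SAP 4.11 the bullet on missing times says it serves the 72-hour rule; the cause bullet does not, and may govern only which bleeds enter the spontaneous endpoint. This stands too. But a blank does not match a traumatic etiology either, so the SAP still needs to say how a blank is compared.

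**Safeguards exist.** Investigators review bleed records with patients (SAP 2.2.2), discrepant data are queried (protocol 7.1), all bleeds are listed with a flag for those not counted separately (SAP 2.2.2.3), and SAP 4.6.6 includes an analysis without the 72-hour rule. These should make blanks less common and splitting or merging more visible. They do not show the effect of the relabelling.

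**The default is conservative and the shift small.** Calling unknown causes spontaneous raises the reported rate against the drug. For 2% to 10% missing, the illustrative rise of about 0.03 to 0.16 is small beside the quoted interval of 0.7 to 2.2. This stands and sets the severity. It supports the default where nothing is known about the cause, not where the database holds one.

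A reader might infer that the rule inflates the treated-bleed and all-bleed ABRs by double counting. The documents do not support that: wrong merges are as possible as wrong splits.

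**Conclusion.** The rule in SAP 4.11 conflicts with SAP 2.2.2.6 for any bleed with a missing cause whose number is on the trauma form. For those bleeds the treated spontaneous rate is biased upward, apart from records absorbed by a nearby same-site spontaneous bleed. If the imputed label is also used as etiology in the 72-hour rule, treated-bleed and all-bleed counts can be wrong in either direction.

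The size cannot be determined. A reader might take the rise from 1.30 to 1.38 at 5% missing as the size of the defect. It is that only if every such bleed is trauma-linked, and the 5% is itself an assumption.

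Severity is minor: efficacy is a secondary objective, all analyses are descriptive (SAP 4), and the default works against the drug.

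**What to change.** Replace the bullet in SAP 4.11 with a short sequence:

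1. If the cause is missing and the bleed number appears on the trauma form, set the cause to traumatic.
2. Set the remaining missing causes to spontaneous.
3. Apply this derived cause before the 72-hour rule.
4. Report the number of causes imputed by step 1 and by step 2.

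I would not also treat an unlinked blank as matching the preceding bleed at the same site. That could only lower counts, in the drug's favor. It would also conflict with step 2 and with the selection order in SAP 2.2.2.9: a record merged into a traumatic bleed for one endpoint would still count as spontaneous for another.

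The cost is SAP wording, one merge of forms already collected and a slightly longer derivation. No new data are needed.
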